SA 1. To develop a tailored (MEET-ME) and a non-tailored (NTHP) HIV/AIDS prevention intervention focused on addressing the partner-seeking behaviors of single YMSM (ages 18-24).

SA 2. To conduct usability testing of the MEET-ME (N=10) and NTHP (N=6) interventions and collect preliminary data on the feasibility, acceptability, and intervention content in preparation for a small pilot randomized control trial (RCT).

SA 3. To test a small pilot RCT of the refined MEET-ME (N=120) intervention as compared to the NTHP (N=60) intervention, in order to evaluate its feasibility and acceptability and gather preliminary efficacy results

NCT02842060

in promoting HIV risk reduction behaviors (e.g., consistent condom use, decreased UAI partners and occasions, and more HIV/STI testing).

SIGNIFICANCE

Interventions specific to YMSM are needed to curtail the rise of new HIV/AIDS infections. More than 60% of all new HIV infections are transmitted through sexual contact among MSM²⁰. In 2010, YMSM accounted for 72% of new infections among people ages 13 to 24, and 30% of all new infections among MSM²⁰. Consistent with the National HIV/AIDS Strategy for the United States' call to reduce new HIV infections by intensifying prevention efforts in highly-impacted communities²¹, we propose an intervention that promotes HIV prevention behaviors (e.g., condom use, reduction in number of unprotected anal intercourse (UAI), HIV/STI testing) among single YMSM reporting recent UAI in the prior 6 months.

At present, there are few efficacy-tested online HIV prevention interventions for YMSM. Most of the existing evidence-based interventions (EBIs) for MSM (e.g., Many Men, Many Voices; MPowerment; d-up!) are delivered in face-to-face group settings. This format creates difficulties for YMSM when they cannot easily access these EBIs in their communities, are not able to attend the sessions when they are offered, and cannot choose to engage with the interventions' content when most convenient. Increasingly, YMSM report their desire to access comprehensive sexual education through the Internet^{22,23} given their increased use of social media in day-to-day interactions and the ease of accessing needed information at the desired time through tablets, laptops, and smartphones. Collocating online interventions is also important as YMSM often rank the web as their top resource to explore their sexuality, learn about MSM behavior, and refine their interests²⁴⁻²⁶.

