
Intervention Description. The proposed intervention will consist of a 6-session web-based program (henceforth referred to a MEET-ME). Cognizant of challenges maintaining users' attention in a web application and to facilitate delivery through a smartphone, we will design each session to be no more than 20 minutes in length. In the course of these 6 sessions, YMSM will have a total of 120 minutes of intervention exposure. Across sessions, we will emphasize the importance of sexual decision-making across different partner types, help YMSM consider what type of relationship(s) they want, and align these relationship desires with safer sex practices. At the end of each session, participants in both intervention conditions will answer a brief acceptability assessment. Participants will have to wait 24 hours to unlock the next session in order to ensure that they avoid cognitive burnout and have time to think through the content offered in each session.

Once participants have completed the baseline assessment (see Measures below), YMSM randomized to the MEET-ME intervention will receive their personalized tailored content based on their demographic information (e.g., race/ethnicity, age), partner-seeking behaviors and relationship desires, and prior sexual attitudes and behaviors (e.g., decisional balance, UAI). In line with Hawkin's framework⁷⁰, tailored content will match HIV/AIDS prevention messages and safer sex skills with YMSM's outcome expectancies when meeting new partners and thereby help them consider how to integrate safer sex practices into different partner types. This approach aims to maximize content persuasiveness and relevance and facilitate behavior change by

NCT02842060

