After completing each session, participants will be directed to a brief "MEET-ME" activity. These activities will be developed and designed to build their HIV risk reduction skills, promote self-reflection about YMSM's sexual health, and consider how their partner-seeking behaviors and sexual decision-making may promote or hinder the achievement of these relationships. We will develop finalized activities alongside the YAB members; however, we foresee interactive activities that help YMSM role play scenarios and negotiate condom use with hookups, friends with benefits, and romantic interest; describe their ideal relationships, including short-term and long-term relationships; develop their own list of sex and relationship rules and strategies to stick to them, respectively; and contrast how these expectations and rules align with their prior partner-seeking and sexual behaviors. We will program the online modules and activities so that YMSM may compare whether their answers are consistent with the tailored suggestions, and revisit content and/or revise their answers to reinforce the material. Participants will be able to print and/or email these activities as a reference.

Attention-Control Condition Description. We will create a 6-session web-based attention-control comparison to match MEET-ME in time and attention yet have *non-tailored* and non-interactive content (NTHP). Similar to the design used in KEEP IT Up!⁷⁹, NTHP will include HIV/STI information currently available on sex education websites. CHCR will also be responsible for the design and development of the NTHP so as to avoid confounding due to aesthetics and site features. Our attention-control condition allows us to avoid confounding due to content (i.e., comparing MEET-ME to a non-HIV "health promotion" intervention) and ensures that all YMSM receive *some* HIV prevention content given their high vulnerability to HIV. Further, this

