comparison will help us critically examine the extent to which tailoring increases YMSM's acceptability to the program, above and beyond having a non-tailored, non-interactive intervention. We acknowledge that the comparison condition will make it harder to detect an intervention effect in our outcome assessments; however, consistent with the R34 guidelines, we are seeking to test the intervention's feasibility and acceptability and to estimate critical parameters required for adequate power estimation in a subsequent large scale RCT trial, even if we are unable to detect small differences between conditions (see "Power Analysis" below).

Phase 2: Testing the Design and Interface through Usability Evaluation. Pilot testing for acceptability and feasibility will occur for both the MEET-ME and NTHP interventions. To develop, refine, and standardize the interventions, we will use best practices in usability testing⁸⁰ to examine the developed interventions.

Recruitment. We will recruit 16 YMSM to participate in our usability evaluation. Candidates must (1) be male at birth and identify as male, (2) ages 18 to 24 (inclusive), (3) self-report as single, (4) self-report as HIV-negative, (5) have had UAI with a male partner in the past 6 months, and (6) live in Southeast Michigan.

Table 1. Sampling Plan	Age	
	18-20	21-24
Race/Ethnicity		
White/Caucasian	3	3
Black/African American	3	3
Asian American/Pacific Islander	1	1
Hispanic/Latino	1	1

We will employ a stratified purposive sampling strategy to ensure racial/ethnic diversity across participants based on their race/ethnicity and age group (see Table 1). This racial/ethnic distribution is commensurate to diversity in the area. We will apply several recruitment strategies, including study promotion through online LGBT listservs, flyers in HIV/AIDS community-based organizations,

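### The two-arm comparison is said to show what tailoring adds to acceptability, but the control also lacks interactivity, so the gain cannot be credited to tailoring alone

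*Combined protocol and SAP*

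**What the plan says.** All references are to the combined protocol and SAP.

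- **The claim.** Attention-Control Condition Description says that the "comparison will help us critically examine the extent to which tailoring increases" participants' acceptance of the programme. The same sentence names as reference an intervention with neither tailoring nor interactivity.
- **The control.** The same section builds NTHP as six web sessions "to match MEET-ME in time and attention", with content that is neither tailored nor interactive. On topic it says that "NTHP will include HIV/STI information currently available on sex education websites".
- **The activities.** Intervention Description says of MEET-ME: "After completing each session, participants will be directed to a brief" MEET-ME activity. The foreseen examples are interactive, including role plays on negotiating condom use with different partner types.
- **Exposure.** Intervention Description limits each session to 20 minutes and says "YMSM will have a total of 120 minutes of intervention exposure" over the six sessions.
- **The aim.** SA 1 reads: "To develop a tailored (MEET-ME) and a non-tailored (NTHP) HIV/AIDS prevention intervention focused on addressing the partner-seeking behaviors of single YMSM (ages 18-24".
- **The analysis.** The model under Estimation of parameters for a subsequent R01 has one treatment variable, equal to 1 for MEET-ME and 0 for NTHP.

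**The concern.** The claim names one ingredient, tailoring, as the cause of any gain in acceptability. The design changes at least one other ingredient, interactivity, at the same time. Interactive delivery could raise ratings by itself: the SEF asks whether the programme was interesting, relevant to the participant's life and instructive, and role plays could move those answers with no tailoring at all.

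This matters because acceptability is a stated aim (SA 3), Innovation presents tailoring as the novel element, and the pilot data are to guide changes to the intervention before a larger trial. If a gain that came from interactivity were credited to tailoring, the wrong feature might be protected or extended.

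Two points in the description of the arms add to the uncertainty about what is being compared. SA 1 and the control description can be read differently on whether NTHP covers partner-seeking. The plan also does not say whether the post-session activities fall inside the counted exposure time.

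**Working it through.** **1. The arms side by side**

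| Feature | MEET-ME | NTHP | How firm is the difference? |
|---|---|---|---|
| Tailoring | Yes | No | Explicit |
| Interactivity of content | Yes | No | Explicit, in the sentence describing the control and again in the claim |
| Post-session activities | Yes, interactive | None described | Strongly implied: they carry the MEET-ME name and the control is non-interactive. They overlap with the row above |
| Partner-seeking and relationship topics | Yes (session outlines) | Unclear | Not settled: SA 1 can be read as including them, and no NTHP session outline is given |
| Time and attention | Six sessions, 120 minutes | To match MEET-ME | Match promised; status of activity time not stated |
| End-of-session acceptability assessment | Yes | Yes | Stated to be common to both |

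The last row helps in reading the third: where a post-session element applies to both arms, the plan says so.

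**2. What the contrast can estimate**

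Let T indicate tailoring and I interactivity (including the activities). Write mean acceptability as

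μ + τT + ιI + θTI.

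- MEET-ME has T = 1, I = 1, so its mean is μ + τ + ι + θ.
- NTHP has T = 0, I = 0, so its mean is μ.
- The difference is D = τ + ι + θ.

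This is one equation in three unknowns, or in two if there is no interaction (θ = 0). T and I take the same values as the treatment variable in every participant, so a model containing both is rank-deficient.

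For scale only, take D = 0.37, the Table 4 detectable difference for N=180 and rho=.6 (any value would do). With θ = 0:

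- τ = 0.37, ι = 0 gives D = 0.37
- τ = 0.185, ι = 0.185 gives D = 0.37
- τ = 0, ι = 0.37 gives D = 0.37

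The data cannot distinguish these cases. A larger sample narrows the interval for D and tells us nothing about the split.

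**3. Whether anything else in the plan separates them**

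No third arm, factor or analysis does. The model with the single treatment variable is written for the longitudinal outcomes, and no separate acceptability model is described. Acceptability Assessments does log which interactive features are clicked, but such use is chosen by participants and not randomised.

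The plan names two safeguards. Confounding by content is said to be avoided, but only in the sense of not using a non-HIV control. Confounding by aesthetics and site features is addressed by having the same centre develop both sites, yet interactivity is itself a feature on which the sites differ by design.

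**4. Exposure time**

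6 sessions × 20 minutes = 120 minutes, which reproduces the stated total. The sessions at their maximum length use all of it. The activities follow the sessions and have no stated length, so the text leaves open whether they lie inside or outside the 120 minutes.

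**The case against.** The strongest reply is that this is only wording. The sentence that makes the claim also discloses that the control is non-interactive. The plan treats interactive elements as part of how it tailors: content-matching can send participants with low self-efficacy to an interactive activity, and the activities let users compare their answers with tailored suggestions. Tailoring may then be shorthand for the whole tailored, interactive programme. SA 3, the Phase 3 description and the treatment variable all compare MEET-ME with NTHP, no tailoring-only effect is powered, and the proposed next step is a large trial of the intervention as a whole.

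Much of this stands. The package contrast is already the trial's comparison, and no analysis has to change. What does not stand is that disclosure cures the attribution. The sentence names two differences and credits the gain to one, and a report that followed it would draw a conclusion the design cannot support.

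A reader might also infer more than the documents support:

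- **That behavioural effects are likewise credited to tailoring.** The sentence concerns acceptability only.
- **That the arms are known to differ in relationship content.** This is inferred. The plan says what NTHP will include, not that it contains nothing else, and SA 1 points the other way.
- **That the time match fails.** The activities are called brief, 20 minutes is a ceiling, the 120 minutes describes MEET-ME, and NTHP is committed to matching MEET-ME whatever its length. A gap is unresolved, not shown.
- **That there is a long list of separate differences.** The activities are themselves interactive, so counting them separately from interactivity counts some of the same thing twice.

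**Conclusion.** The concern holds for the acceptability claim. As designed, a MEET-ME advantage on the SEF or CSQ-8 is the joint effect of tailoring and interactivity, including the activities. The share due to tailoring is not identified at any sample size. This rests on the explicit statement that NTHP is both non-tailored and non-interactive and on the two-arm design; it needs no assumption about activity length or NTHP topics.

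The reach is limited. The comparison of MEET-ME with NTHP is valid as a comparison of two programmes, and the feasibility and parameter-estimation aims are unaffected. The partner-seeking focus of NTHP and the place of activity time are ambiguities to settle, not demonstrated imbalances. The change should be made because following the present text would lead to an unsupported conclusion about tailoring.

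**What to change.** 1. In Attention-Control Condition Description, state the acceptability contrast and its conclusion as the MEET-ME package (tailored, interactive, with post-session activities) versus non-tailored, non-interactive NTHP. Remove the claim about tailoring alone.
2. Reconcile SA 1 with the control description: say whether NTHP addresses partner-seeking or is limited to existing HIV/STI information.
3. State whether activity time falls within the 120 minutes and whether it is included in the time match.
4. Report logged time by arm, including the activities. Time spent in each session is already tracked under Acceptability Assessments; confirm that the log covers the activities.

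The cost is a few sentences and one descriptive table by arm. No new arm, participants or model is needed.

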Although we will employ recommended strategies to avoid loss to FU⁹¹, we project a conservative attrition rate of 20% by the 90-day FU; however, we will use this R34 as an opportunity to estimate an attrition rate specific to MEET-ME. These data will help identify who may be more vulnerable to loss to FU, and how to develop retention strategies for the subsequent trial. We will compare those who completed each FU interview with those who did not on key predictors to characterize the profile of non-responders. Missing data generated from recording errors will be minimized due to the computer-based entry for all measures. The generalized linear mixed model analysis that we will conduct for the longitudinal outcome data is valid under missing at random mechanism. The use of Intent to Treat (ITT) principle for the longitudinal analyses will also aid to overcome missing data concerns when appropriate⁹².

Data Collection. We will use MTS' web survey feature to collect YMSM's data. Web surveys allow participants to complete the survey at a convenient location (e.g., home, friend's house), circumvent barriers (e.g., scheduling, transportation) present in interviewer-administered or phone-based interviews, and decrease social desirability. Participants will be able to earn up to \$70 total (VISA e-cards; Baseline= \$30, FU1 = \$15, FU2 = \$20, and FU3 = \$25). We backloaded the FU incentives to encourage completion of all three data collection time points and reduce participant attrition over time. Participants will create a username and password, allowing them to log into the different sessions and complete the surveys (or return to them later if they are interrupted). To maximize completion, participants will receive e-mail and/or text reminders. See Human Subjects section for a comprehensive description of the protections and safety procedures embedded into our web-survey data collection.

Acceptability Assessments. Acceptability data will be collected right after completing each intervention session. We will use two different assessments: (1) Intervention Evaluation Forms (SEF)⁹³ and (2) Client Satisfaction Questionnaires (CSQ-8)⁹⁴. The SEF is a brief 13-item questionnaire that elicits information about the participant's experience with the intervention (i.e., was the intervention interesting, was it relevant to their life, did they learn from the intervention). The CSQ-8 will be used at the completion of the intervention and at

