Psychological risk correlates. We will measure *depression*, *anxiety*, and *loneliness* symptoms as markers of psychological distress. Depression and anxiety symptoms in the past week will be measured using the Brief Symptom Inventory¹⁰⁵. Both scales include 6 items rated on a 5-point scale (1=never, 5 = very often), respectively. We will use the UCLA Loneliness scale¹⁰⁶ to measure feelings of loneliness (1=Never;4=Often). We will also measure *self-esteem* using Rosenberg’s scale¹⁰⁷, a 10-item measure using a 5-point scale. We will measure *internalized homophobia*¹⁰⁸ with 12 items measured on a 4-point scale (0=Strongly disagree; 3=Strongly agree). Finally, we will measure *sexuality-related stressors* using a 9-item scale (0=never/4=3+ times) with strong reliability¹⁰⁹ assessing the frequency of discriminatory events (e.g., verbal insults) due to someone knowing/assuming YMSM were gay/bisexual.

Data Analyses. Prior to conducting our multivariate analyses, we will examine study variables using descriptive statistics and test for differences across demographic characteristics (e.g., race/ethnicity, age, education) using t-tests, ANOVAs, and Chi-squares, as appropriate. As participants will be randomized to the two treatment groups, systematic baseline differences are not expected; however, in the event that some parameters differ across conditions at baseline, they will be included as covariates in subsequent multivariate models. We will calculate descriptive summary statistics corresponding to the study variables at each visit to understand any temporal patterns, as well as compare the two treatment groups in terms of average change from baseline after intervention (averaged across all three FU times).

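### Model covariates are chosen by chance baseline imbalance, so predictors of outcome and dropout need not enter the GLMM that is called valid under MAR

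*Combined protocol and SAP*

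**What the plan says.** All places are in the combined protocol and SAP.

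- **Phase 3, Recruitment (attrition and missing data).** One overall loss figure is given: "we project a conservative attrition rate of 20% by the 90-day FU". Completers and non-completers are then compared: "We will compare those who completed each FU interview with those who did not on key predictors to characterize the profile of non-responders". The predictors are not listed and arm is not mentioned. The stated use is: "These data will help identify who may be more vulnerable to loss to FU, and how to develop retention strategies for the subsequent trial". The one attrition rate named as an estimate is in the words "we will use this R34 as an opportunity to estimate an attrition rate specific to MEET-ME".
- **Same section, validity claim.** "The generalized linear mixed model analysis that we will conduct for the longitudinal outcome data is valid under missing at random mechanism". The intent-to-treat principle is offered as further help: "The use of Intent to Treat (ITT) principle for the longitudinal analyses will also aid to overcome missing data concerns when appropriate".
- **Data Analyses, covariates.** Systematic baseline differences are not expected because of randomisation, but "in the event that some parameters differ across conditions at baseline, they will be included as covariates in subsequent multivariate models".
- **Estimation of parameters for a subsequent R01, model.** The GLMM has an unspecified covariate term, visit, treatment, their interaction and a random intercept. The baseline outcome is either a repeated response or a covariate.

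No section names auxiliary variables, weighting, imputation or a missing-data sensitivity analysis.

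**The concern.** A likelihood-based mixed model gives valid estimates under MAR conditional on the observed outcomes and the covariates in the model. The claim is therefore only as good as the covariate set. Here the set is decided by a trigger unrelated to the missing-data problem. A variable can be balanced between arms, predict the outcome and predict loss, and never meet the trigger. Another can differ by chance, predict nothing, and enter.

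Arm-specific dropout is plausible: the control site is non-tailored and non-interactive by design. At stake are a modest bias in the preliminary arm contrast and some avoidable loss of precision. The candidate variables are already collected at baseline (Table 3). Intent-to-treat does not fill the gap: it settles who is analysed in which arm, not what the model must condition on when outcomes are missing.

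**Working it through.** **1. Yardstick from the plan.** With m = 4 observations, SD 1, rho = .6, 120 and 60 men, two-sided alpha .05 and 80% power:

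d = (1.960 + .842) x sqrt{[(1 + 3 x .6)/4] x (1/120 + 1/60)} = 2.802 x sqrt(.70 x .025) = .371.

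Table 4 gives .37, so it reproduces.

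**2. Illustrative scenario (assumptions, not figures from the documents).** No true arm effect; rho = .6. A baseline trait is held by 30% of men and raises the follow-up outcome by g = .3, .5 or .8 SD. MEET-ME loses 15% whatever the trait. Control loses 60% of men with it and 17% of those without.

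- Control loss: .3 x .60 + .7 x .17 = .299, about 30%.
- Overall loss: (120 x .15 + 60 x .30)/180 = 36/180 = 20%, the plan's figure.

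**3. Rough ceiling.** Among control completers the trait share is .3 x .40/.701 = .171; in MEET-ME it stays .30. Comparing only men seen at the last visit would be biased by about (.300 - .171) x g = .039, .064 and .103 SD. The plan does not do this; it uses all visits.

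**4. Planned type of model.** Follow-up outcome on visit, arm, baseline value and a random intercept. I ran 4,000 replicates at 120/60, with the dropout visit spread evenly (also assumed):

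| g | Bias, trait omitted | Bias, trait included | SD of estimate, omitted / included |
|---|---|---|---|
| .3 | .017 | .001 | .105 / .104 |
| .5 | .026 | -.002 | .110 / .104 |
| .8 | .040 | -.001 | .119 / .105 |

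A separate run of the scenario gave .016, .028 and .042 with the trait omitted and about 0 with it included. The SD fell from .104 to .095 (g = .5) and from .120 to .102 (g = .8).

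In units of the SD of the estimate, the bias is .017/.105 = .16, .026/.110 = .24 and .040/.119 = .34. Against the detectable effect of .37, .04 SD is 11%.

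**5. Dependence on the mechanism.** Large-sample runs kept baseline as a repeated outcome, with a continuous predictor, no true effect and about 20% loss in each arm.

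- Same dropout mechanism in both arms: bias .003.
- Predictor acts in MEET-ME only: -.059.
- Opposite directions by arm: -.115, or -.037 if the predictor has no extra effect at follow-up.
- Strongly opposite (log odds ratio +1.2 and -1.2 per SD): -.231.
- Predictor and its interaction with the post-baseline period included: within .005 of zero throughout.

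The sign follows from the direction assumed.

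**6. Precision of attrition at 20% loss.**

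- MEET-ME 24/120: 95% CI (Wilson) 13.8% to 28.0%.
- Control 12/60: 11.8% to 31.8%.
- Half-width for the difference: 1.96 x sqrt(.16/120 + .16/60) = .124, or 12.4 points.

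**The case against.** The strongest reply is that the documents are silent on several points rather than wrong, and that the effect is small.

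- **Profiling.** A reader might infer that dropout is profiled only in the pooled sample. The text does not mention arm, and arm could be one of the unlisted predictors. What can be said is that no by-arm comparison is specified.
- **Covariates.** A reader might infer that a variable can enter only if it is imbalanced. The rule says imbalanced variables will be included; it does not bar others, and the GLMM's covariate term is open. The Innovation section also names demographics, distress and substance use as influences on the modelled associations. What stands is that imbalance is the only selection rule stated and that dropout predictors are nowhere carried into the model.
- **Control attrition.** A reader might infer that it will not be estimated. The words "estimate an attrition rate specific to MEET-ME" follow the projected 20% and may simply mean study-specific. Both arms are assessed at every visit, and proportions with 95% CIs are planned for key parameters. The control rate is unnamed, not excluded.
- **Size.** The GLMM already conditions on observed outcomes. The bias needs an arm-specific mechanism, is below half a standard error, and this is a pilot that declines to base effect sizes on its own data. All of this stands. It makes the point a cheap improvement, not a threat to the trial.
- **A data-driven remedy.** Choosing covariates from the within-arm dropout profile would rest on about 12 control dropouts at 20% loss and would replace one data-driven rule with another. That is right, and the fix avoids it.

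**Conclusion.** The point holds in limited form. Selecting covariates by observed baseline imbalance is the weaker method, because under randomisation imbalance is chance and unrelated to prognosis or dropout, while the MAR claim depends on what is in the model.

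Under the assumed scenario the bias is about .02 to .04 SD, under half a standard error at n=180, and including the variable removes it. Precision improves as well: in the two stronger settings the SD of the estimate falls by about 5 to 9% (.110 to .104; .104 to .095) and 12 to 15% (.119 to .105; .120 to .102). In the weakest setting it hardly moves. The bias is nil if dropout works alike in both arms. The larger values, up to .23 SD, need strong opposite mechanisms by arm that nothing in the documents suggests, and I do not rest the point on them. Only a continuous outcome was simulated; counts and testing rates were not.

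The documents do not support saying that the primary comparison is invalid, that dropout predictors are barred from the model, or that control attrition will go unreported.

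**What to change.** 1. In Data Analyses, replace the imbalance-triggered rule with a short fixed set used in every GLMM: the baseline value of the outcome plus a few baseline variables expected to predict outcome and loss, for example age group, race/ethnicity, substance use and psychological distress. Where baseline is modelled as a repeated outcome, add the interactions of these variables with visit; main effects alone would not capture an association that differs between baseline and follow-up.
2. As a minor addition, report attrition at each visit by arm, with the arm difference and 95% CIs. Estimate rather than test, given the half-width of about 12 points.
3. Do not choose primary-model covariates from the within-arm dropout profile; use it in a sensitivity model at most.

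Cost: SAP wording, one or two tables and a few degrees of freedom out of 180 men. In logit models the odds ratio becomes conditional on the added covariates, so the SAP should say so and the next trial's planning should use the figure accordingly. No new data collection is needed.
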